APPENDIX E ECOG PERFORMANCE STATUS

Grade	Description
0	Normal activity, fully active, able to carry on all predisease performance without restriction.
1	Symptoms, but fully ambulatory, restricted in physically strenuous but ambulatory and able to carry out work of a light or sedentary nature (e.g., light housework, office work).
2	Ambulatory and capable of all self-care but unable to carry out any work activities. Up and about more than 50% of waking hours.
3	Capable of only limited self-care, confined to bed or chair more than 50% of waking hours.
4	Completely disabled. Cannot carry on any self-care. Totally confined to bed or chair.
5	Dead

Source: [Oken 1982](#).

Eastern Cooperative Oncology Group, **PPD** MD, Group Chair.

**APPENDIX F NEW YORK HEART ASSOCIATION (NYHA)
CLASSIFICATION**

- Class I: Patients with no limitation of activities; they suffer no symptoms from ordinary activities.
- Class II: Patients with slight, mild limitation of activity; they are comfortable with rest or with mild exertion.
- Class III: Patients with marked limitation of activity; they are comfortable only at rest.
- Class IV: Patients who should be at complete rest, confined to bed or chair; any physical activity brings on discomfort and symptoms occur at rest.

APPENDIX G SUMMARY OF INTERNATIONAL MYELOMA WORKING GROUP UNIFORM RESPONSE CRITERIA (IMWG-URC)

Summary of International Myeloma Working Group Uniform Response Criteria (IMWG-URC)

Response Subcategory ^a	Multiple Myeloma Response Criteria
sCR ^b	
 • CR as defined below and • Normal SFLC ratio and • Absence of clonal cells in bone marrow by immunohistochemistry or immunofluorescence^c
CR ^{b, h}	
 • Negative immunofixation on the serum and urine and • Disappearance of any soft tissue plasmacytomas and • < 5% plasma cells in bone marrow
VGPR ^b	
 • Serum and urine M-protein detectable by immunofixation but not on electrophoresis or • ≥ 90% reduction in serum M-protein with urine M-protein level < 100 mg/24 hours • If the serum and urine M-protein are not measurable, a decrease of ≥ 90% in the difference between the involved and uninvolved FLC levels required in place of the M-protein criteria. However, documentation of VGPR requires collection and analysis of 24 hour urine sample for UPEP and immunofixation and confirmed to be negative. • If present at baseline, a ≥ 50% reduction in the size of soft tissue plasmacytomas is also required.
PR ^b	
 • ≥ 50% reduction of serum M-protein and reduction in 24-hour urinary M-protein by ≥ 90% or to < 200 mg/ 24 h • If the serum and urine M-protein are unmeasurable, a ≥ 50% decrease in the difference between involved and uninvolved FLC levels is required in place of the M-protein criteria. • If serum and urine M-protein are not measurable, and serum free light assay is also not measurable, ≥ 50% reduction in plasma cells is required in place of M-protein, provided baseline bone marrow cell percentage was ≥ 30% • If present at baseline, a ≥ 50% reduction in the size of soft tissue plasmacytomas is also required
MR	
 • 25%–49% reduction in the level of serum M-protein and a 50%–89% reduction in 24 hour urinary M-protein, which still exceeds 200 mg per 24 hours • If the serum and urine M-protein are not measurable, a decrease of 25%–49% in the difference between involved and uninvolved FLC levels is required in place of the M-protein criteria. • If present at baseline, a 25%–49% reduction in the size of soft tissue plasmacytomas is also required
Stable disease	
 • Not meeting criteria for sCR, CR, VGPR, PR, MR, or PD

Summary of International Myeloma Working Group Uniform Response Criteria (IMWG-URC) (cont'd)

Response Subcategory ^a	Multiple Myeloma Response Criteria
PD ^b	
Any one or more of the following:
 
 • Increase of $\geq 25\%$ from lowest response value in: 
 ○ Serum M-component and/or (the absolute increase must be ≥ 0.5 g/dL) ○ Urine M-component and/or (the absolute increase must be ≥ 200 mg/24 h) ○ Only in patients without measurable serum and urine M-protein levels; the difference between involved and uninvolved FLC levels. The absolute increase must be >10 mg/dL ○ Bone marrow plasma cell percentages (absolute percentage must be $\geq 10\%$) • Definite development of new bone lesions or soft tissue plasmacytomas or definite increase in the size of existing bone lesions or soft tissue plasmacytomas^{e, f, g} • Development of hypercalcemia (corrected serum calcium > 11.5 mg/dL or 2.65mmol/L) that can be attributed solely to the plasma cell proliferative disorder

Source: Durie 2006; Rajkumar 2011 (modified for protocol purposes).

CR = complete response; sCR = stringent complete response; FLC = serum light chain; PD = progressive disease; PR = partial response; sFLC = serum free light chain; VGPR = very good partial response.

Note: For patients without measurable protein on UPEP at baseline, UPEP will need to be repeated to confirm a response of VGPR or better.

- ^a Patients with measurable disease in both serum (SPEP) and urine (UPEP) at study entry are required to meet response criteria in both UPEP and SPEP in order to qualify for a MR or better. Conversely, it should be noted that criteria for PD only needs to be met, and confirmed, in one parameter.
- ^b All response categories (CR, sCR, VGPR, PR) require 2 consecutive assessments made at any time before the institution of any new therapy, as well as no known evidence of progressive or new bone lesions if radiographic studies were performed. Radiographic studies are not required to satisfy these response requirements. Bone marrow, plasmacytoma, and skeletal survey assessments are not required to be confirmed by repeat testing. SD requires a duration of ≥ 6 weeks.
- ^c Presence/absence of clonal cells is based upon the κ/λ ratio. An abnormal κ/λ ratio by immunohistochemistry and/or immunofluorescence requires a minimum of 100 plasma cells for analysis. An abnormal ratio reflecting presence of an abnormal clone is κ/λ of $> 4:1$ or $< 1:2$.
- ^d Determination of PD while on study requires 2 consecutive assessments made at any time before classification of PD and/or the institution of new therapy. Serum M-component increases of ≥ 1 g/dL from nadir are sufficient to define progression if nadir M-component is ≥ 5 g/dL.
- ^e Plasmacytomas: A definite increase in the size is defined as a $\geq 50\%$ increase as measured serially by the sum of the products of the cross-diameters of the measurable lesion. A plasmacytoma is considered measurable if the longest diameter is at least 1 cm and the product of the cross diameters is at least 1 cm². Plasmacytomas of lesser size will be considered non-measurable.
- ^f The requirement for bi-directional measurements applies only to plasmacytomas.
- ^g The plasmacytoma specifications for PD are based on the Sponsor's interpretation of the IMWG-URC and practical considerations for study execution.
- ^h In patients with sFLC measurable disease only, normal sFLC ratio is required for CR.

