10.3 MULTIPLE MYELOMA RESPONSE ASSESSMENTS

10.3.1 *DISEASE RESPONSE AND PROGRESSION ASSESSMENTS*

Determination of disease response must be based on the reported values from the central laboratory. Local laboratory results may be used for hypercalcemia (corrected calcium based on albumin), but a confirmatory sample should be collected and sent to the central laboratory for documentation.

Investigator-determined responses must be based on results from the central laboratory and must be consistent with the IMWG-URC (see definitions in [Appendix G](#)).

10.3.2 *TUMOR RESPONSE ASSESSMENT*

The following confirmatory assessments are required for all response categories (sCR, CR, VGPR, PR, minimal response [MR] and PD; refer to definitions in [Appendix G](#):

- All laboratory-based PD (except bone marrow sample) and all response categories require 2 consecutive assessments made at any time before initiation of new therapy.
- All response categories require that there be no evidence of disease progression, including confirmation of no new bone lesions, if radiographic studies were performed.
- The preferred method of confirming CR or sCR is a bone marrow biopsy; however, a bone marrow aspirate is also acceptable for confirmation of CR.
- Extramedullary plasmacytoma evaluation (if present at Screening). Two consecutive radiographic tests are not required to confirm response or progression of extramedullary plasmacytoma.
- In the case where a patient does not have measurable M-protein by UPEP at baseline (i.e., baseline UPEP < 200 mg/24 hours), when SPEP is consistent with response (i.e., ≥ PR), 2 consecutive UPEP measurements must be performed to confirm response.

10.3.3 *DISEASE PROGRESSION*

Disease progression will be documented in an eCRF intended to capture PD information and will be analyzed as a study endpoint. Signs and symptoms related to disease progression (e.g., pathologic fracture in a subject with progressive multiple myeloma) should be reported in the appropriate eCRF as an AE or as an SAE (if the event in question meets the criteria for seriousness). Verbatim terms such as “disease progression,” “progressive disease,” etc. should not be reported as AEs or SAEs unless

the investigator considers the progression to be atypical, accelerated, or caused by the study drug. Similarly deaths occurring as a result of disease progression should be reported on the eCRF intended to capture death information and should not be reported as SAEs.

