Study treatment should not be discontinued on the basis of disease progression, until PD has been appropriately confirmed per IMWG-URC. Disease progression during LTFU must also be confirmed by these same criteria. Confirmation of PD will require 2 consecutive central laboratory evaluations that indicate PD, except in cases where PD is based on extramedullary lesions or hypercalcemia that is attributed solely to PD. These assessments should be separated in time by at least 1 calendar day, but no more than 28 ± 4 calendar days. Local laboratory results may not be used to determine or confirm disease progression, except when PD is based on hypercalcemia. The assessments outlined in [Appendix B](#) are required for PD determination.

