7.7 Subgroup Analyses

Exploratory subgroup analyses for the primary endpoint and key secondary endpoints (ORR and OS) will be performed for each level of the three randomization stratification factors: International Staging System (ISS) Stage at study entry (Stage 1 vs. Stage 2 or 3), Refractory to bortezomib treatment (Yes vs. No) and Age (< 65 vs. \geq 65 years, <75 vs. \geq 75). Additional subgroup analyses will be based on the following factors:

- Sex (male vs. female)
- Race (White vs. Asian vs. Other)
- Ethnicity (Hispanic or Latino vs. Not Hispanic or Latino)
- Geographic region (Europe vs. North America vs. Asian Pacific)
- Baseline ECOG (0 vs. 1)
- Baseline creatinine clearance (30 < 50 ml/min vs. 50 < 80 ml/min vs. ≥ 80 ml/min)
- FISH risk group (high risk vs. standard risk vs. unknown)
- β2 microglobulin level (< 3.5 mg/L vs. ≥ 3.5 mg/L)
- ISS stage at baseline (Stage I vs. Stage II and III)
- ISS stage at diagnosis (Stage I vs. Stage II and III vs. Unknown)
- Corrected calcium at baseline (≤11.5 mg/dL vs. >11.5 mg/dL)
- Lines of prior treatment (2 vs. 3)
- Prior transplant (Yes vs. No)
- Prior lenalidomide (Yes vs. No)
- Refractory to lenalidomide (Yes vs. No)

These subgroups, except for stratification variables, will be re-examined and appropriately re-categorized before unblinding. Subgroup analysis containing a subgroup of less than 5% of the whole population will not be conducted.

8. Interim Analysis and Early Stopping Guidelines

One interim analysis will be conducted for PFS when approximately 263 (75% of total 350) PFS events are observed. The objective of the interim analysis is to monitor for differences between treatment arms for evidence of a substantial benefit in the carfilzomib once-weekly with dexamethasone arm.

To ensure proper control of type I error rate, the interim and final analysis of PFS will be analyzed under a group sequential design framework with the stopping boundaries constructed using the Lan-DeMets spending function with an O'Brien-Fleming approach. The stopping boundaries in an example scenario are calculated using East 6.4 and presented in Table 3. Actual boundaries will be calculated on the basis of observed PFS events up to the data cut-off date for the interim analysis.

Statistical Analysis Plan: 20140355

Date: 09 Jun 2017 Page 23

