Appendix B. Reference Values/Toxicity Grades

Laboratory Values

Safety laboratory values below a distinct limit (eg. detection limit, documented as "< [limit]") will be substituted by half of the limit and values above a distinct limit (documented as "> [limit]") will be substituted by the limit itself for all analyses.

A Grade (based on CTC AE version 4.0 [v4.03: June 14, 2010]) will be assigned to each laboratory result as detailed in Table 2. Depending on the toxicity definition, the same result may be assigned to two grading for deviations towards higher or lower values. Values not meeting any of the criteria will be assigned a grade 0.

Table 2. Grading of Select Laboratory Parameters

Table 2. Grading of Select Laboratory Parameters							
Laboratory Abnormality [Unit]	Grade 1	Grade 2	Grade 3	Grade 4			
Decreased Lymphocytes [G/L]	0.8 - < LLN	0.5 - < 0.8	0.2 - < 0.5	< 0.2			
Decreased Neutrophils [G/L]	1.5 - < LLN	1.0 - < 1.5	0.5 - < 1.0	< 0.5			
Decreased Platelets [G/L]	75 - < LLN	50 - < 75	25 - < 50	< 25			
Decreased WBC [G/L]	3.0 - < LLN	2.0 - < 3.0	1.0 - < 2.0	< 1.0			
Decreased Hemoglobin [g/L]	100 - < LLN	80 - < 100	< 80	not defined			
Decreased Albumin [g/L]	30 - < LLN	20 - < 30	< 20	not defined			
Increased AST	> ULN – 3*ULN	> 3*ULN – 5*ULN	> 5*ULN – 20*ULN	> 20*ULN			
Increased ALT	> ULN – 3*ULN	> 3*ULN – 5*ULN	> 5*ULN – 20*ULN	> 20*ULN			
Increased Total Bilirubin	> ULN – 1.5*ULN	>1.5*ULN – 3*ULN	> 3*ULN – 10*ULN	> 10*ULN			
Increased Creatinine	>1 - 1.5 * BL or >ULN -	>1.5 - 3.0 * BL or >1.5 -	>3.0 * BL or >3.0 - 6.0 *	>6.0 * ULN			
	1.5 *ULN	3.0 * ULN	ULN				
Decreased Corrected Calcium [mmol/L]	2.0 - < LLN	1.75 - < 2.0	1.5 - < 1.75	< 1.5			
Increased Corrected Calcium [mmol/L]	>ULN - 2.9	>2.9 – 3.1	>3.1 – 3.4	>3.4			
Decreased Potassium [mmol/L]*	3.0 - < LLN	3.0 - < LLN; symptomatic; intervention indicated	2.5 - < 3.0	< 2.5			

Statistical Analysis Plan: 20140355

Date: 09 Jun 2017 Page 42

Laboratory Abnormality				
[Unit]	Grade 1	Grade 2	Grade 3	Grade 4
Increased Potassium [mmol/L]	5.5 - >ULN	>5.5 – 6.0	>6.0 – 7.0	>7.0
Decreased Sodium[mmol/L]	130- <lln< td="">not defined	120-<130	<120	</lln<>	not defined	120-<130	<120
Increased Sodium[mmol/L]	>ULN-150	>150-155	>155-160	>160
Decreased Phosphorus [mmol/L]	0.8 - <lln< td="">0.6 - <0.8	0.3 - <0.6	<0.3	</lln<>	0.6 - <0.8	0.3 - <0.6	<0.3
Increased Magnesium [mmol/L]	>ULN – 1.23	not defined	>1.23 – 3.30	>3.30

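### Appendix G prints the hypercalcaemia progression limit as two different values: 11.5 mg/dL is 2.87 mmol/L, not 2.65 mmol/L

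*Protocol*

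**What the plan says.** PFS is the primary endpoint, and PD is one of its two components (Protocol 13.1.1). Appendix G treats any single criterion in its PD list as sufficient. One of them is "Development of hypercalcemia (corrected serum calcium > 11.5 mg/dL or 2.65mmol/L) that can be attributed solely to the plasma cell proliferative disorder".

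Protocol 10.3.1 requires investigators' assessments to agree with Appendix G. Section 10.3.3 ties PD to patient management: "Study treatment should not be discontinued on the basis of disease progression, until PD has been appropriately confirmed per IMWG-URC". It also lets sites use their own calcium values: "Local laboratory results may not be used to determine or confirm disease progression, except when PD is based on hypercalcemia".

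The SAP uses both units for corrected calcium. Section 7.7 sets a subgroup cut in mg/dL, "Corrected calcium at baseline (≤11.5 mg/dL vs. >11.5 mg/dL", while the toxicity grading table in SAP Appendix B is in mmol/L.

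Primary PFS rests on the computational assessment (ORCA). SAP Section 6 says that its detailed rules are in a separate specification, built on the published myeloma criteria and the protocol.

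On confirmation of PD, 10.3.3 asks for two consecutive central evaluations, "except in cases where PD is based on extramedullary lesions or hypercalcemia that is attributed solely to PD". The general sentence in 10.3.2 reads "All laboratory-based PD (except bone marrow sample) and all response categories require 2 consecutive assessments" and does not mention calcium. The same section separately excepts plasmacytoma: "Two consecutive radiographic tests are not required to confirm response or progression of extramedullary plasmacytoma".

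**The concern.** A limit printed in two units should give the same answer in either. This one does not. Two careful readers could apply Appendix G to the same blood result and disagree on whether the subject has progressed, depending only on the unit in which the laboratory reports.

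Both units may well be in use. The trial plans about 150 sites worldwide (Protocol 4.2), SAP 7.7 names Europe, North America and Asia Pacific as regions, and local calcium is allowed for this criterion. That some sites report in mg/dL and others in mmol/L is an inference, but a reasonable one.

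At stake is whether, and when, a calcium-based PD is called. The lower limit would add such events or bring them forward. The higher limit would omit or delay them. The same call can lead a site to stop treatment.

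**Working it through.** **Inputs.** From Protocol Appendix G: 11.5 mg/dL and 2.65 mmol/L. The molar mass of calcium is a physical constant that the documents do not give. I take 40.078 g/mol and show the range 40.0 to 40.08.

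**Formula.** mmol/L = (mg/dL × 10) / molar mass. With 40.078, 1 mmol/L = 4.0078 mg/dL.

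**Attempt to reproduce the printed figure.**
- 11.5 × 10 / 40.078 = 2.869 mmol/L (2.869 to 2.875 over the range). The protocol prints 2.65, so the figure is not reproduced.
- In reverse, 2.65 × 4.0078 = 10.62 mg/dL (10.60 to 10.62 over the range).

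**Size of the gap.**
- 2.869 − 2.65 = 0.219 mmol/L.
- 11.5 − 10.62 = 0.88 mg/dL, and 0.88 / 11.5 = 7.6%.

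**Could rounding or another unit explain it?**
- Anything that rounds to 11.5 mg/dL (11.45 to 11.55) is 2.857 to 2.882 mmol/L.
- Anything that rounds to 2.65 mmol/L (2.645 to 2.655) is 10.60 to 10.64 mg/dL. The ranges do not meet.
- To get 2.65, the molar mass would have to be 115 / 2.65 = 43.4 g/mol.
- Read as mEq/L, 11.5 mg/dL would be 2.869 × 2 = 5.74, which does not match either.

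**What it does to one subject.** A corrected calcium of 11.0 mg/dL is 11.0 / 4.0078 = 2.74 mmol/L. It is below 11.5, so it is not PD in mg/dL. It is above 2.65, so it is PD in mmol/L. The same holds for every value above 10.62 and up to 11.5 mg/dL. Reading the printed *or* as two alternative limits does not help: 10.62 mg/dL would then always decide, and the figure of 11.5 would have no function.

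**Which figure is meant?** The documents do not say outright. The only other place where either value appears as a corrected-calcium cut is SAP 7.7, which uses 11.5 mg/dL. That favours 11.5, although it is a baseline subgroup and does not define PD.

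**The case against.** The arithmetic is hard to dispute; the case on the other side is about consequence.

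- **Primary PFS may be untouched.** ORCA decides it, and its specification may already carry one limit. This stands: no effect on primary PFS has been shown. But the SAP names the protocol as one of ORCA's sources, so the faulty line is among its inputs, and a check is warranted.
- **One central laboratory, one unit.** Response is judged on central results, and SAP 9.2 names a single vendor. This carries weight, but 10.3.1 and 10.3.3 make an exception for local calcium.
- **The SAP's two units prove little.** One is a baseline subgroup and the other is toxicity grading. Neither shows PD being judged in mmol/L. This is fair; the error lies in Appendix G and does not depend on the SAP.
- **The figure may come from the cited criteria.** Appendix G adapts published criteria, and their text is not available here. No source can make the two values equal, however, and the table is described as modified for this protocol.

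A reader might go further and infer that the SAP has no confirmation rule for PD in PFS. The documents do not support that. SAP 3.1 follows subjects up to confirmed PD. Table 1 fixes the event date, which is compatible with dating a confirmed PD at its first assessment.

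A reader might also see a serious conflict in the calcium waiver of confirmation. Section 10.3.3 is the specific rule on progression and states the waiver plainly. The SAP Section 6 exception list, which omits calcium, governs only investigator-assessed best response. What remains is that the general sentence in 10.3.2 does not match 10.3.3, which is a point of wording.

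**Conclusion.** The limit is wrong as written. It is one threshold for a component of the primary endpoint, printed as two values 0.22 mmol/L (0.88 mg/dL) apart. That holds for any plausible molar mass of calcium.

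The consequence is probably small. It is confined to subjects whose corrected calcium lies above 10.62 and up to 11.5 mg/dL, with the rise attributed to myeloma alone. The documents do not give their number.

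It would be tempting to infer that the treatment comparison is biased or underpowered. Neither follows. The criterion is the same in both arms. The final analysis is triggered at about 350 PFS events (or by the end of 2018 if earlier), and the lower limit would add events. An effect on primary PFS is possible but cannot be judged without the ORCA specification. This is a threshold correction of small consequence.

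**What to change.** Before unblinding:

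1. State one limit in Appendix G, correct in both units. For example, > 11.5 mg/dL (2.87 mmol/L), which agrees with the SAP 7.7 cut-point.
2. Check that the ORCA and IRC specifications use that limit.
3. Review any calcium-based PD calls already made, and record how a call in the disputed band is handled.
4. As an editorial matter only, add hypercalcaemia due solely to PD to the exceptions in the general sentence of 10.3.2, so that it agrees with 10.3.3.

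The cost is one corrected number, one added exception, a check of two specifications and a review of what are probably few calls. No new data or visits are needed. If the change is treated as substantive, Protocol 15.1 sends it to health authorities and ethics committees, so with about 150 sites it is best combined with another amendment if the timing allows.

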APPENDIX H INTERNATIONAL STAGING SYSTEM

The International Staging System (ISS) for myeloma was published by the International Myeloma Working Group ([Greipp 2005](#)):

Stage	Criteria
I	Serum beta-2 microglobulin < 3.5 mg/L and serum albumin ≥ 3.5 g/dL
II	Serum beta-2 microglobulin < 3.5 mg/L and serum albumin < 3.5 g/dL or Serum beta-2 microglobulin 3.5–5.5 mg/L irrespective of the serum albumin
III	Serum beta-2 microglobulin ≥ 5.5 mg/L

**APPENDIX I NATIONAL CANCER INSTITUTE COMMON TERMINOLOGY
CRITERIA FOR ADVERSE EVENTS (NCI-CTCAE) GRADING SCALE**

Common Terminology Criteria for Adverse Events (CTCAE) of the
National Cancer Institute (NCI), Version 4.03

Published: 28 May 2009 (v4.03: June 14, 2010)

http://evs.nci.nih.gov/ftp1/CTCAE/CTCAE_4.03_2010-06-14_QuickReference_8.5x11.pdf

APPENDIX J PATIENT REPORTED OUTCOMES

CCI

APPENDIX K COUNTRY SPECIFIC PREGNANCY AND CONTRACEPTIVE SUPPLEMENT

A woman of childbearing potential (WOCBP) is defined as:

Any woman who has experienced menarche and is not postmenopausal or permanently sterilized. Permanent sterilization methods include hysterectomy, bilateral salpingectomy, and bilateral oophorectomy.

A postmenopausal woman is defined as:

- Age > 55 years with cessation of menses for 12 or more months
- Age < 55 years but no spontaneous menses for at least 2 years
- Age < 55 years and spontaneous menses within the past 1 year, but currently amenorrheic (e.g., spontaneous or secondary to hysterectomy), and with postmenopausal gonadotropin levels (luteinizing hormone and follicle-stimulating hormone levels > 40 IU/L) or postmenopausal estradiol levels (< 5 ng/dL) or according to the definition of "postmenopausal range" for the laboratory involved.
- Underwent a bilateral oophorectomy

Pregnancy Prevention Information

Female Subjects

Highly effective methods of birth control are defined as methods that achieve a failure rate of less than 1% per year when used consistently and correctly.

WOCBP must use a highly effective method of birth control during treatment and for an additional 30 days after the last dose of protocol-required therapies. Highly effective methods of birth control for female participants or their male partner include:

- Combined (estrogen and progestogen) hormonal methods: pills, vaginal ring, or skin patch.
- Single hormonal methods (progestogen to stop the release of the egg from the ovary): pills, shots/injections, implants (placed under the skin by a healthcare provider)
- Intrauterine device (IUD)
- Intrauterine hormonal-releasing system (IUS) surgery to tie both fallopian tubes (bilateral tubal ligation/occlusion)

- Vasectomised partner: Provided the partner is the sole sexual partner of the WOCBP trial participant and that the vasectomized partner has received medical assessment of the surgical success.
- Sexual abstinence: Refraining from heterosexual intercourse during the entire period of risk associated with the study treatment. The reliability of sexual abstinence needs to be evaluated in relation to the duration of the clinical trial and with the preferred and usual lifestyle of the subject.

Male Subjects

If the male subjects sole female partner has received medical confirmation that she is postmenopausal or she has had a permanent sterilization method (hysterectomy, bilateral oophorectomy, or bilateral salpingectomy) or the male subject has had a vasectomy with medical confirmation of surgical success, or his sole female partner has had a bilateral tubal ligation/occlusion, additional contraceptive methods are not required during this study. Otherwise, if the male subject's female partner could become pregnant, the male must:

- Practice true sexual abstinence. (Refraining from heterosexual intercourse during treatment and for an additional 90 days following the last dose of study drug administration. The reliability of sexual abstinence needs to be evaluated in relation to the duration of the clinical trial and be the preferred and usual lifestyle of the subject.)

Or

- Use a condom with spermicide during treatment and for an additional 90 days following the last dose of study drug administration. (Note a condom without spermicide is acceptable in countries where spermicide is not commercially available.)

The female partner should also consider using an acceptable method of effective contraception such as:

- Intrauterine device (IUD)
- Intrauterine hormonal-releasing system (IUS)
- Hormonal birth control method: pill, shots/injections, implants (placed under the skin by a healthcare provider), skin patches, or a vaginal ring
- Female barrier method: diaphragm, cervical cap, or contraceptive sponge (a female condom is not an option because there is a risk of tearing when both partners use a condom)

Male subjects must not donate sperm during treatment and for an additional 90 days following the last dose of study drug administration.

Males with pregnant partners must practice true sexual abstinence or wear a condom during vaginal sex to prevent exposure to the embryo/fetus through semen.

